3.2 Exclusion Criteria

- **3.2.1** Is currently participating or has participated in a study of investigational agent or using an investigational device with 30 days of the first dose of pembrolizumab.
- **3.2.2** a. Has had prior chemotherapy, targeted small molecule therapy, or radiation therapy within 3 weeks prior to study Day 1
 - b. Subjects must have recovered (i.e., \leq Grade 1 or at baseline) from any adverse events due to a previously administered agent. Subjects with \leq Grade 2 neuropathy are an exception to this criterion and may qualify for the study.
 - c. If subject received major surgery, they must have recovered adequately from the toxicity and/or complications from the intervention prior to starting therapy.
- **3.2.3** Is receiving systemic steroid therapy within three days prior to the first dose of pembrolizumab or receiving any other form of immunosuppressive medication
- **3.2.4** Is expected to require any other form of systemic or localized antineoplastic therapy while on trial.
 - Subjects with ER+/PR+ disease may be given endocrine therapy.
 - Subjects with HER2+ disease will be required to discontinue trastuzumab (Herceptin).
- **3.2.5** Has participated in another MK03475 trial.
 - **3.2.5.1** Note: Patients with or without prior PARP-inhibitor exposure may be included.
- 3.2.6 Concomitant use of known strong CYP3A inhibitors (eg. itraconazole, telithromycin, clarithromycin, protease inhibitors boosted with ritonavir or cobicistat, indinavir, saquinavir, nelfinavir, boceprevir, telaprevir) or moderate CYP3A inhibitors (eg. ciprofloxacin, erythromycin, diltiazem, fluconazole, verapamil). The required washout period prior to starting olaparib is 2 weeks.
- 3.2.7 Concomitant use of known strong (eg. phenobarbital, enzalutamide, phenytoin, rifampicin, rifabutin, rifapentine, carbamazepine, nevirapine and St John's Wort) or moderate CYP3A inducers (eg. bosentan, efavirenz, modafinil). The required washout period prior to starting olaparib is 5 weeks for enzalutamide or phenobarbital and 3 weeks for other agents.

- **3.2.8** Major surgery within 2 weeks of starting study treatment and patients must have recovered from any effects of any major surgery.
- **3.2.9** Has known hypersensitivity to pembrolizumab or any of its excipients
- **3.2.10** Has a known additional malignancy that is progressing or requires active treatment. Exceptions include basal cell carcinoma of the skin, squamous cell carcinoma of the skin, or in situ cervical cancer that has undergone potentially curative therapy.
- **3.2.11** Has known history of prior malignancy except if the patient has undergone potentially curative therapy with no evidence of that disease recurrence for 5 years since initiation of that therapy.
- **3.2.12** Has known active central nervous system (CNS) metastases and/or carcinomatous meningitis. Subjects with previously treated brain metastases may participate provided they are stable (without evidence of progression by MRI for at least four weeks prior to the first dose of pembrolizumab and any neurologic symptoms have returned to baseline), have no evidence of new or enlarging brain metastases, and are using no steroids for at least three days prior to study medication.
- 3.2.13 Has evidence of interstitial lung disease or active, non-infectious pneumonitis
- 3.2.14 Has active tuberculosis
- **3.2.15** Resting ECG indicating uncontrolled, potentially reversible cardiac conditions, as judged by the investigator (eg., unstable ischemia, uncontrolled symptomatic arrhythmia, congestive heart failure, QTcF prolongation >500 ms, electrolyte disturbances, etc.), or patients with congenital long QT syndrome.
- **3.2.16** Persistent toxicities (>Common Terminology Criteria for Adverse Event (CTCAE) grade 2) caused by previous cancer therapy, excluding alopecia.
- **3.2.17** Patients with myelodysplastic syndrome/acute myeloid leukaemia or with features suggestive of MDS/AML.
- **3.2.18** Patients unable to swallow orally administered medication and patients with gastrointestinal disorders likely to interfere with absorption of the study medication.
- **3.2.19** Patients with a known hypersensitivity to olaparib or any of the excipients of the product.
- **3.2.20** Has received a live vaccine or live-attenuated vaccine within 30 days prior to the first dose of pembrolizumab. Administration of killed vaccines is allowed.
- **3.2.21** Has a known history of Human Immunodeficiency Virus (HIV) (HIV 1/2 antibodies). Has known active Hepatitis B (e.g., HBsAg reactive) or Hepatitis C (e.g., HCV RNA [qualitative] is detected).
- 3.2.22 Has an active autoimmune disease that has required systemic treatment in the past 2 years (i.e. with use of disease modifying agents, corticosteroids or immunosuppressive drugs). Subjects with vitiligo or resolved childhood asthma/atopy would be exception to this rule. Subjects that require inhaled steroid or local steroid injections will not be excluded from the study. Subjects with hypothyroidism not from autoimmune disease and stable on hormone replacement will not be excluded from the study. Note: Replacement therapy (eg., thyroxine, insulin, or physiologic

corticosteroid replacement therapy for adrenal or pituitary insufficiency, etc.) is not considered a form of systemic treatment.

- **3.2.23** Has had an allogenic tissue / solid organ transplant.
- **3.2.24** Previous allogenic bone marrow transplant or double umbilical cord blood transplantation (dUCBT).
- **3.2.25** Has a history or current evidence of any condition, therapy, or laboratory abnormality that might confound the results of the trial, interfere with the subject's participation for the full duration of the trial, or is not in the best interest of the subject to participate, in the opinion of the treating Investigator.
- **3.2.26** Has known psychiatric or substance abuse disorders that would interfere with cooperation with the requirements of the trial.
- 3.2.27 Is pregnant or breastfeeding, or expecting to conceive or father children within the projected duration of the trial, starting with the screening visit (Visit 1) through 120 days after the last dose of study treatment.

4.0 TREATMENT PLAN

4.1 Treatment Dosage and Administration

This is an open-label, single-arm pilot study in 20 subjects with advanced BRCA mutation or HDR-defect associated breast cancer having progressed through standard first line therapy.

The study participation is up to 35 administrations of pembrolizumab (approximately two years).

Pembrolizumab and olaparib will be supplied by Merck.

Pembrolizumab will be administered at a dose of 200mg as a 30 minute IV infusion Q3W. Effort should be made to target infusion timing to be as close to 30 minutes as possible. However, given the variability of infusion pumps, a window of -5 minutes and +10 minutes is permitted (i.e., infusion time is 30 minutes: -5 min/+10 min).

Olaparib 300mg will be self-administered orally twice daily. The dose of olaparib used in this study is 300 mg twice daily which is the currently approved dose. Subjects will complete a compliance diary throughout the study treatment period. Olaparib tablets should be taken at the same time each day, approximately 12 hours apart with one glass of water. The tablets should be swallowed whole and not chewed, crushed, dissolved or divided. Olaparib tablets can be taken with or without food. Each container will be labelled in accordance with Good Manufacturing Practice (GMP) Annex 13 and per country regulatory requirement. If vomiting occurs shortly after the olaparib tablets are swallowed, the dose should only be replaced if all of the intact tablets can be seen and counted. Should any patient enrolled on the study miss a scheduled dose for whatever reason (e.g., as a result of forgetting to take the tablets or vomiting), the patient will be allowed to take the scheduled dose up to a maximum of 2 hours after that scheduled dose time. If greater than 2 hours after the scheduled dose time, the missed dose is not to be taken and the patient should take their allotted dose at the next scheduled time.

The Pharmacy Manual contains specific instructions for pembrolizumab dose calculation, reconstitution, preparation of the infusion fluid, and administration.

Table 2. Trial Intervention

Drug Dose/Potency	Dose/	Route of	Regimen/ Treatment
-------------------	-------	----------	--------------------

		Frequency	Administration	Period
Pembrolizumab	200 mg	Q3W	IV infusion	Day 1 of each cycle
Olaparib	300mg	BID	PO	Continuous; dispensed
				each cycle day 1 (each
				cycle=3 weeks)

4.1.1 Meals and dietary restrictions

It is prohibited to consume grapefruit juice while on olaparib therapy.

4.2 Toxicities, Dosing Delays, and Dose Modifications

4.2.1 Pembrolizumab

If a dose of pembrolizumab is withheld for toxicity, then subjects may resume dosing with pembrolizumab if that is appropriate at their next scheduled appointment or when toxicity has improved as described below.

Pembrolizumab will be withheld for drug-related Grade 4 hematologic toxicities, nonhematological toxicity ≥ Grade 3 including laboratory abnormalities, and severe or life-threatening adverse events.

AEs associated with pembrolizumab exposure, including coadministration with additional compounds, may represent an immunologic aetiology. These immune-related AEs (irAEs) may occur shortly after the first dose or several months after the last dose of pembrolizumab/combination treatment and may affect more than one body system simultaneously. Therefore, early recognition and initiation of treatment is critical to reduce complications. Based on existing clinical study data, most irAEs were reversible and could be managed with interruptions of pembrolizumab/combination treatment, administration of corticosteroids and/or other supportive care. For suspected irAEs, ensure adequate evaluation to confirm etiology or exclude other causes. Additional procedures or tests such as bronchoscopy, endoscopy, skin biopsy may be included as part of the evaluation. Dose modification and toxicity management guidelines for irAEs associated with pembrolizumab/combination treatment are provided in Table 3.

Attribution of Toxicity:

When study interventions are administered in combination, attribution of an adverse event to a single component is likely to be difficult. Therefore, while the investigator may attribute a toxicity event to the combination, to olaparib alone, or to pembrolizumab alone, for adverse events listed in Table 3, both interventions must be held according to the criteria in Table 3 Dose Modification and Toxicity Management Guidelines for Immune-Related Adverse Events Associated with Pembrolizumab.

Holding Study Interventions:

When study interventions are administered in combination, if the AE is considered immune-related, both interventions should be held according to recommended dose modifications.

Restarting Study Interventions:

Participants may not have any dose modifications (no change in dose or schedule) of pembrolizumab in this study, as described in Table 3.

If the toxicity does not resolve or the criteria for resuming treatment are not met, the participant must be discontinued from all study interventions.

If the toxicities do resolve and conditions are aligned with what is defined in Table 3, the combination of olaparib and pembrolizumab may be restarted at the discretion of the investigator. In these cases where the toxicity is attributed to the combination or to

olaparib alone, re-initiation of pembrolizumab as a monotherapy may be considered at the principal investigator's discretion.

Dosing Interruptions:

Dosing interruptions are permitted in the case of medical / surgical events or logistical reasons not related to study therapy (e.g., elective surgery, unrelated medical events, patient vacation, and/or holidays). Subjects should be placed back on study therapy within 3 weeks of the scheduled interruption, unless otherwise discussed with the Sponsor. The reason for interruption should be documented in the patient's study record.

Table 3: Dose Modification and Toxicity Management Guidelines for Immune-related AEs Associated with Pembrolizumab monotherapy and IO combinations

General instructions:

- 1. Severe and life-threatening irAEs should be treated with IV corticosteroids followed by oral steroids. Other immunosuppressive treatment should begin if the irAEs are not controlled by corticosteroids.
- 2. Study intervention must be permanently discontinued if the irAE does not resolve or the corticosteroid dose is not ≤10 mg/day within 12 weeks of the last study intervention treatment.
- 3. The corticosteroid taper should begin when the irAE is \leq Grade 1 and continue at least 4 weeks.
- 4. If study intervention has been withheld, study intervention may resume after the irAE decreased to ≤ Grade 1 after corticosteroid taper.

irAEs	Toxicity Grade (CTCAE v5.0)	Action With Pembrolizumab	Corticosteroid and/or Other Therapies	Monitoring and Follow-up
	Grade 2	Withhold	• Administer corticosteroids (initial dose of 1 to 2 mg/kg prednisone or equivalent)	Monitor participants for signs and symptoms of pneumonitis
Pneumonitis	Recurrent Grade 2, Grade 3 or 4	Permanently discontinue	 followed by taper Add prophylactic antibiotics for opportunistic infections 	Evaluate participants with suspected pneumonitis with radiographic imaging and initiate corticosteroid treatment
Diarrhea/Colitis	Grade 2 or 3	Withhold	Administer corticosteroids (initial dose of 1 to 2 mg/kg prednisone or equivalent) followed by taper	Monitor participants for signs and symptoms of enterocolitis (ie, diarrhea, abdominal pain, blood or mucus in stool with or without fever) and of bowel perforation (ie, peritoneal signs

irAEs	Toxicity Grade (CTCAE v5.0)	Action With Pembrolizumab	Corticosteroid and/or Other Therapies	Monitoring and Follow-up
	Recurrent Grade 3 or Grade 4	Permanently discontinue		 Participants with ≥Grade 2 diarrhea suspecting colitis should consider GI consultation and performing endoscopy to rule out colitis Participants with diarrhea/colitis should be advised to drink liberal quantities of clear fluids. If sufficient oral fluid intake is not feasible, fluid and electrolytes should be substituted via IV infusion
AST or ALT Elevation or	Grade 2 ª	Withhold	Administer corticosteroids (initial dose of 0.5 to 1 mg/kg prednisone or equivalent) followed by taper	Monitor with liver function tests (consider weekly or more frequently until liver enzyme value returned to baseline or is stable)
Increased Bilirubin	Grade 3 b or 4 c	Permanently discontinue	Administer corticosteroids (initial dose of 1 to 2 mg/kg prednisone or equivalent) followed by taper	
T1DM or Hyperglycemia	New onset T1DM or Grade 3 or 4 hyperglycemia associated with evidence of β-cell failure	Withhold ^d	 Initiate insulin replacement therapy for participants with T1DM Administer antihyperglycemic in participants with hyperglycemia 	Monitor participants for hyperglycemia or other signs and symptoms of diabetes

irAEs	Toxicity Grade (CTCAE v5.0)	Action With Pembrolizumab	Corticosteroid and/or Other Therapies	Monitoring and Follow-up	
	Grade 2	Withhold	Administer corticosteroids and initiate hormonal replacements as clinically	Monitor for signs and symptoms of hypophysitis (including hypopituitarism and adrenal)	
Hypophysitis	Grade 3 or 4	Withhold or permanently discontinue d	indicated	insufficiency)	
	Grade 2	Continue	Treat with nonselective beta-blockers (eg, propranolol) or thionamides as	Monitor for signs and symptoms of thyroid disorders	
Hyperthyroidism	Grade 3 or 4	Withhold or permanently discontinue d	appropriate		
Hypothyroidism	Grade 2, 3 or 4	Continue	Initiate thyroid replacement hormones (eg, levothyroxine or liothyronine) per standard of care	Monitor for signs and symptoms of thyroid disorders	
Nephritis: grading	Grade 2	Withhold	Administer corticosteroids (prednisone 1)	Monitor changes of renal function	
according to increased creatinine or acute kidney injury	Grade 3 or 4	Permanently discontinue	to 2 mg/kg or equivalent) followed by taper		
Neurological	Grade 2	Withhold	Based on severity of AE administer corticosteroids	Ensure adequate evaluation to confirm etiology	
Toxicities	Grade 3 or 4	Permanently discontinue		and/or exclude other causes	
	Grade 1	Withhold	Based on severity of AE administer	Ensure adequate evaluation to confirm etiology	
Myocarditis	Grade 2, 3 or 4	Permanently discontinue	corticosteroids	and/or exclude other causes	

irAEs	Toxicity Grade (CTCAE v5.0)	Action With Pembrolizumab	Corticosteroid and/or Other Therapies	Monitoring and Follow-up
Exfoliative	Suspected SJS, TEN, or DRESS	Withhold	Based on severity of AE administer corticosteroids	Ensure adequate evaluation to confirm etiology or exclude other causes
Dermatologic Conditions	Confirmed SJS, TEN, or DRESS	Permanently discontinue		
	Persistent Grade 2	Withhold	Based on severity of AE administer	Ensure adequate evaluation to confirm etiology
All Other irAEs	Grade 3	Withhold or discontinue based on the event e	corticosteroids	or exclude other causes
	Recurrent Grade 3 or Grade 4	Permanently discontinue		

AE(s)=adverse event(s); ALT= alanine aminotransferase; AST=aspartate aminotransferase; CTCAE=Common Terminology Criteria for Adverse Events; DRESS=Drug Rash with Eosinophilia and Systemic Symptom; GI=gastrointestinal; IO=immuno-oncology; ir=immune related; IV=intravenous; SJS=Stevens-Johnson Syndrome; T1DM=type 1 diabetes mellitus; TEN=Toxic Epidermal Necrolysis; ULN=upper limit of normal.

Note: Non-irAE will be managed as appropriate, following clinical practice recommendations.

- ^a AST/ALT: >3.0 to 5.0 x ULN if baseline normal; >3.0 to 5.0 x baseline, if baseline abnormal; bilirubin:>1.5 to 3.0 x ULN if baseline normal; >1.5 to 3.0 x baseline if baseline abnormal
- b AST/ALT: >5.0 to 20.0 x ULN, if baseline normal; >5.0 to 20.0 x baseline, if baseline abnormal; bilirubin: >3.0 to 10.0 x ULN if baseline normal; >3.0 to 10.0 x baseline if baseline abnormal
- ^c AST/ALT: >20.0 x ULN, if baseline normal; >20.0 x baseline, if baseline abnormal; bilirubin: >10.0 x ULN if baseline normal; >10.0 x baseline if baseline abnormal
- d The decision to withhold or permanently discontinue pembrolizumab is at the discretion of the investigator or treating physician. If control achieved or ≤ Grade 2, pembrolizumab may be resumed.
- e Events that require discontinuation include, but are not limited to: encephalitis and other clinically important irAEs (eg, vasculitis and sclerosing cholangitis).

Dose modification and toxicity management of infusion-reactions related to pembrolizumab

Pembrolizumab may cause severe or life-threatening infusion-reactions including severe hypersensitivity or anaphylaxis. Signs and symptoms usually develop during or shortly after drug infusion and generally resolve completely within 24 hours of completion of infusion. Dose modification and toxicity management guidelines on pembrolizumab associated infusion reaction are provided in Table 4.

Table 4 Pembrolizumab Infusion Reaction Dose modification and Treatment Guidelines

NCI CTCAE Grade	Treatment	Premedication at Subsequent Dosing
Grade 1	Increase monitoring of vital signs as medically indicated until the participant is	None
Mild reaction; infusion interruption	deemed medically stable in the opinion of the investigator.	
not indicated; intervention not		
indicated		
Grade 2	Stop Infusion.	Participant may be premedicated 1.5h (± 30 minutes)
Requires therapy or infusion	Additional appropriate medical therapy may include but is not limited to:	prior to infusion with:
interruption but responds promptly	IV fluids	Diphenhydramine 50 mg po (or equivalent dose of
to symptomatic treatment (e.g.,	Antihistamines	antihistamine).
antihistamines, NSAIDs, narcotics,	NSAIDs	Acetaminophen 500-1000 mg po (or equivalent dose
IV fluids); prophylactic medications	Acetaminophen	of analgesic).
indicated for ≤24 hrs	Narcotics	
	Increase monitoring of vital signs as medically indicated until the participant is	
	deemed medically stable in the opinion of the investigator.	
	If symptoms resolve within 1 hour of stopping drug infusion, the infusion may be	
	restarted at 50% of the original infusion rate (e.g. from 100 mL/hr to 50 mL/hr).	
	Otherwise dosing will be held until symptoms resolve and the participant should be	
	premedicated for the next scheduled dose.	
	Participants who develop Grade 2 toxicity despite adequate premedication	
Grades 3 or 4	should be permanently discontinued from further study drug treatment	No cube a superior de cine
Grades 3 or 4 Grade 3:	Stop Infusion.	No subsequent dosing
	Additional appropriate medical therapy may include but is not limited to:	
Prolonged (i.e., not rapidly	Epinephrine** IV fluids	
responsive to symptomatic medication and/or brief interruption	Antihistamines	
of infusion); recurrence of	NSAIDs	
symptoms following initial	Acetaminophen	
improvement; hospitalization	Narcotics	
indicated for other clinical sequelae	Oxygen	
(e.g., renal impairment, pulmonary	Pressors	
infiltrates)	Corticosteroids	
""""des	Increase monitoring of vital signs as medically indicated until the participant is	
Grade 4:	deemed medically stable in the opinion of the investigator.	
Life-threatening; pressor or	Hospitalization may be indicated.	
ventilatory support indicated	**In cases of anaphylaxis, epinephrine should be used immediately.	
- commission outpost managed	Participant is permanently discontinued from further study drug treatment.	
Appropriate resuscitation equipment	should be available at the bedside and a physician readily available during the period of	drug administration.

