4.2.3.2 Management of non-haematological toxicity

Repeat dose interruptions are allowed as required, for a maximum of 4 weeks on each occasion. If the interruption is any longer than this the study monitor must be informed. Where toxicity reoccurs following re-challenge with olaparib, and where further dose interruptions are considered inadequate for management of toxicity, then the patient should be considered for dose reduction or must permanently discontinue olaparib.

Olaparib can be dose reduced to 250 mg twice daily as a first step and to 200 mg twice daily as a second step. Treatment must be interrupted if any NCI-CTCAE grade 3 or 4 adverse event occurs which the investigator considers to be related to administration of study treatment.

Management of new or worsening pulmonary symptom

If new or worsening pulmonary symptoms (e.g., dyspnoea) or radiological abnormalities occur in the absence of a clear diagnosis, an interruption in study treatment dosing is recommended and further diagnostic workup (including a high resolution CT scan) should be performed to exclude pneumonitis.

Following investigation, if no evidence of abnormality is observed on CT imaging and symptoms resolve, then study treatment can be restarted, if deemed appropriate by the investigator. If significant pulmonary abnormalities are identified, these need to be discussed with the Study Physician.

Management of nausea and vomiting

Events of nausea and vomiting are known to be associated with olaparib treatment. These events are generally mild to moderate (CTCAE grade 1 or 2) severity, intermittent and manageable on continued treatment. The first onset generally occurs in the first month of treatment for nausea and within the first 6 months of treatment for vomiting. For nausea, the incidence generally plateaus at around 9 months, and for vomiting at around 6 to 7 months.

No routine prophylactic anti-emetic treatment is required at the start of study treatment, however, patients should receive appropriate anti-emetic treatment at the first onset of nausea or vomiting and as required thereafter, in accordance with local treatment practice guidelines. Alternatively, olaparib tablets can be taken with a light meal/snack (ie 2 pieces of toast or a couple of biscuits). As per international guidance on anti-emetic use in cancer patients (ESMO, NCCN), generally a single agent antiemetic should be considered eg dopamine receptor antagonist, antihistamines or dexamethasone.

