4.4 Supportive Care Guidelines

Subjects should receive appropriate supportive care measures as deemed necessary by the treating investigator. Suggested supportive care measures for the management of adverse events with potential immunologic etiology are outlined below and in greater detail in the ECI guidance document. Where appropriate, these guidelines include the use of oral or intravenous treatment with corticosteroids as well as additional anti-inflammatory agents if symptoms do not improve with administration of corticosteroids. Note that several courses of steroid tapering may be necessary as symptoms may worsen when the steroid dose is decreased. For each disorder, attempts should be made to rule out other causes such as metastatic disease or bacterial or viral infection, which might require additional supportive care. The treatment guidelines are intended to be applied when the investigator determines the events to be related to Pembrolizumab.

Note: if after the evaluation the event is determined not to be related, the investigator is instructed to follow the ECI reporting guidance but does not need to follow the treatment guidance (as outlined in the ECI guidance document). Refer to Section 4.2.1 for dose modification. It may be necessary to perform conditional procedures such as bronchoscopy, endoscopy, or skin photography as part of evaluation of the event. Suggested conditional procedures, as appropriate, can be found in the ECI guidance document.

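### Section 4.2.1's general hold rule conflicts with Table 3, and the protocol does not settle when a Table 3 action applies or to which drug

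*Combined protocol and SAP*

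**What the plan says.** All passages are in the combined protocol and SAP.

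- **General rule, Section 4.2.1:** "Pembrolizumab will be withheld for drug-related Grade 4 hematologic toxicities, nonhematological toxicity ≥ Grade 3 including laboratory abnormalities". The sentence goes on to add severe and life-threatening events.
- **Table 3, hypothyroidism row:** the action at grades 2, 3 and 4 is to continue pembrolizumab. The treatment column reads "Initiate thyroid replacement hormones (eg, levothyroxine or liothyronine) per standard of care".
- **Attribution of Toxicity, Section 4.2.1:** "while the investigator may attribute a toxicity event to the combination, to olaparib alone, or to pembrolizumab alone", the instruction is that "for adverse events listed in Table 3, both interventions must be held according to the criteria in Table 3".
- **Holding Study Interventions, the next paragraph:** "if the AE is considered immune-related, both interventions should be held according to recommended dose modifications".
- **Note under Table 3:** "Note: Non-irAE will be managed as appropriate, following clinical practice recommendations".
- **Table 3 action column:** it is headed for pembrolizumab only. There is no olaparib column.
- **Section 4.2.3.2, olaparib:** "Treatment must be interrupted if any NCI-CTCAE grade 3 or 4 adverse event occurs which the investigator considers to be related" to study treatment. Section 4.2.2 separately allows any toxicity to be managed by interruption or dose reduction.
- **Section 4.4, supportive care:** "The treatment guidelines are intended to be applied when the investigator determines the events to be related to Pembrolizumab". The same section refers dose modification back to Section 4.2.1.

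**The concern.** A site with a toxic event in front of it needs one answer to three questions: does Table 3 apply, what does it require for each drug, and does it override the general rule? The text answers each in more than one way, or not at all. Two investigators could follow the protocol faithfully and treat the same event differently.

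The first stake is patient safety and consistent conduct. The second is efficacy. Section 4.8 makes a patient who does not complete 6 weeks (2 cycles) of both drugs unevaluable for efficacy, and replaces that patient. An early hold made under one paragraph and not under another could therefore change who enters the efficacy set. Section 9.2 takes its stopping decision on 10 patients and its final decision on 20, so one patient is 1/10 = 10 percentage points at the first look and 1/20 = 5 points at the end. The documents give no event frequencies, so the expected effect on the response or clinical benefit rate cannot be sized.

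**Working it through.** No sample-size or error-rate figure is involved. The check sets the rules side by side.

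**Step 1. General rule against the 12 Table 3 categories (pembrolizumab action).** The comparison rule is to withhold at non-haematological grade 3 or above.

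| Table 3 category | Table 3 action | Against the general rule |
|---|---|---|
| Hypothyroidism | Grades 2–4: continue | **Opposed at grades 3–4** |
| Pneumonitis | Grade 2: withhold; recurrent grade 2, or grade 3–4: stop permanently | Earlier; stricter at first grade 3 |
| AST/ALT/bilirubin | Grade 2: withhold; grade 3–4: stop permanently | Earlier; stricter at first grade 3 |
| Nephritis | Grade 2: withhold; grade 3–4: stop permanently | Earlier; stricter at first grade 3 |
| Neurological | Grade 2: withhold; grade 3–4: stop permanently | Earlier; stricter at first grade 3 |
| Myocarditis | Grade 1: withhold; grade 2–4: stop permanently | Earlier; stricter from grade 2 |
| Diarrhoea/colitis | Grade 2–3: withhold; recurrent grade 3, or grade 4: stop permanently | Earlier; stricter at recurrent grade 3 or grade 4 |
| Hypophysitis | Grade 2: withhold; grade 3–4: withhold or stop | Earlier; stricter action optional |
| All other irAEs | Persistent grade 2: withhold; grade 3: withhold or stop; recurrent grade 3, or grade 4: stop permanently | Earlier; stricter at recurrent grade 3 or grade 4 |
| Hyperthyroidism | Grade 2: continue; grade 3–4: withhold or stop | Compatible |
| T1DM/hyperglycaemia | New T1DM, or grade 3–4 hyperglycaemia with beta-cell failure: withhold | Compatible |
| Exfoliative skin conditions | Suspected: withhold; confirmed: stop permanently | Ungraded; no opposition |

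The count is 1 category opposed, 8 that act below grade 3, and 3 with neither feature: 1 + 8 + 3 = 12. Five of the eight (pneumonitis, hepatic, nephritis, neurological, myocarditis) already require permanent discontinuation at a first grade 3 event, where the general rule says only to withhold. For a grade 4 haematological irAE, the general rule withholds and the row for all other irAEs stops permanently.

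**Step 2. Trigger for holding both drugs.** Take grade 2 diarrhoea, attributed to olaparib alone and judged not immune-related.

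| Text | What it requires |
|---|---|
| 4.2.1, Attribution of Toxicity (read literally) | Both drugs must be held: diarrhoea is listed and attribution does not matter |
| 4.2.1, Holding Study Interventions | No hold called for: not immune-related |
| Note under Table 3 | Outside the table; clinical practice |
| 4.2.1, general rule | Not triggered at grade 2 |
| 4.2.3.2 and 4.2.2 | Olaparib interruption not mandatory at grade 2, but permitted |

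The same event is a mandatory hold of both drugs on one reading and discretionary on the others. The verb also changes, from must to should.

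**Step 3. Which drug the action covers.** Take a grade 3 hepatic irAE that later resolves. Table 3 permanently discontinues pembrolizumab. Section 4.2.1 says both drugs are held by the Table 3 criteria, but not whether a permanent stop carries over to olaparib. It removes all study interventions when a toxicity does not resolve or the resumption criteria are not met. It also allows pembrolizumab to restart alone after toxicity attributed to olaparib or to the combination. It does not address olaparib continuing alone after a permanent pembrolizumab stop for an event that has resolved.

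**The case against.** The strongest reply is that the texts can be read together. The attribution sentence ends with the table's full name, which refers to immune-related events, and the table's first column is headed irAEs. Events listed in Table 3 may therefore mean irAEs only. Drug attribution and immune aetiology are also different questions. On that reading the olaparib-attributed, non-immune diarrhoea in Step 2 was never in the table. This is a fair reading, and it makes the trigger an ambiguity and not a flat contradiction. It does not remove the problem, because the sentence expressly covers attribution to olaparib alone and does not repeat the immune-related condition that follows it.

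On grades, the general rule never says to continue below grade 3, and permanent discontinuation includes withholding. The eight earlier or stricter categories can therefore stand as specific additions. That is accepted. It cannot rescue hypothyroidism, where Table 3 is the more permissive text. A convention that the specific text overrides the general one would settle that row, but the protocol does not state one and does not limit the general rule to events outside the table.

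Three stronger readings might be inferred and are not supported:

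- **Section 4.4 as a third hold trigger.** Its condition concerns supportive treatment, and it sends dose modification back to Section 4.2.1. It matters only because Table 3 also carries steroid guidance, so the two conditions for giving that treatment should agree.
- **An instruction to continue both drugs, with no hold, for the Step 2 event.** No passage says this. Section 4.2.2 permits interruption for any toxicity.
- **A loss of at least two infusions on the steroid path.** If onset is just after a day 1 infusion, grade 1 is reached in 7 days and the taper lasts the minimum 28 days, the taper ends at about day 1 + 7 + 28 = 36. Only the day 22 infusion is missed, and day 43 is available.

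**Conclusion.** The point holds, within limits. There is one direct contradiction (hypothyroidism grades 3–4), with no stated order of precedence between the general rule and Table 3. There is one ambiguity with real consequences: whether a Table 3-type event judged not immune-related obliges a hold of both drugs. There is one gap: whether a permanent stop in Table 3 reaches olaparib. The other differences in grade are compatible if Table 3 is read as adding to the general rule, but the reader has to supply that reading.

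The conclusion rests on the wording alone. The ECI guidance document cited in Section 4.4 is not available here and might clarify supportive treatment. No effect on trial results is claimed. The point is worth correcting because it bears on patient safety and is cheap to resolve.

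**What to change.** The sponsor should reconcile Section 4.2.1, Table 3 and its note, Section 4.2.3.2 and Section 4.4 by stating:

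1. one trigger for applying Table 3, saying whether an event attributed to olaparib alone, or judged not immune-related, falls under it, and whether the hold is mandatory;
2. how each Table 3 action, including permanent discontinuation, applies to pembrolizumab and to olaparib;
3. which text takes precedence where the general rule and Table 3 differ, with the hypothyroidism row settled explicitly;
4. a condition for supportive treatment in Section 4.4 that agrees with the steroid guidance in Table 3.

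Which clinical rule stands is for the sponsor to decide; this review proposes none. The cost is a wording amendment, which needs IRB approval before it is implemented (Section 10.8). Sites would need to be told of the change. The sample size and analysis are unaffected.
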